6.1 Risks

Participation in the study includes risks associated with emotional distress related to discussing HIV or HCV status and history of substance use disorder. There is also a risk of possible breach of confidentiality. In terms of emotional distress, participants will be informed that they can choose to not answer some question that might be uncomfortable and end the interview early if he/she were to experience any emotional distress.

There is also a potential risk of breach in confidentiality. We will take steps to prevent this by keeping information in locked cabinets and using computers with password protection.

6.2 Potential Benefits

There will be no direct benefits to participants from taking part in the study; however, the information collected will help improve the care of patients with a history of substance use disorder with or at risk for HIV and HCV.

Participants will receive \$20 for your participation in each interview session with the RA at baseline, 3-and 6 months post-enrollment.

H-39712: Peer Recovery Coaching for Infectious Diseases and Opioid Use Disorder
Version 1.1 07/07/2020

6.3 Analysis of Risks in Relation to Benefits

As noted above, the information collected will help improve the care of patients with a history of substance use disorder with or at risk for HIV and HCV.

7 Study Subject Selection

7.1 Subject Inclusion Criteria

- Inclusion criteria
 - Must be at least 18 years of age at time of enrollment.
 - Individuals with opioid use disorder, non-reactive HIV antibody test and reactive HCV antibody testing at the BMC low-barrier bridge walk-in clinic.
 - Participants providing contact information of two family members or friends.
 - Individuals signing a medical records release form.

7.2 Subject Exclusion Criteria

An individual who meets any of the following criteria will be excluded from participation in this study:

- Individuals unable to provide informed consent
- Unable to speak English
- Individuals already linked to substance use care
- Individuals co-infected with HIV and HCV and engaged in care.

8 Study Intervention

- The intervention: The peer recovery coach with lived experience with recovery from substance use will deliver a semi-scripted brief motivational interview at the time of enrollment. The intervention will last approximately

H-39712: Peer Recovery Coaching for Infectious Diseases and Opioid Use Disorder
Version 1.1 07/07/2020

20 minutes and will take place at the time of the clinical visit while participants are waiting to be seen by a clinician or are awaiting laboratory testing. The intervention will involve the following elements: establishing rapport, asking permission to discuss drugs, discussing the pros and cons associated with drug use, uncovering the gaps between current and desired quality of life and determining readiness to change. Participants will also receive a telephone booster call 5 days following enrollment. The RA will assemble detailed contact information for the patient and will record addresses of two family members or friends. The RA will also collect demographic information and reasons for refusal from individuals who do not participate in the study. Patients seen at the BMC FASTER PATHS bridge clinics usually follow-up at the general medicine clinics at BMC. Following the initial brief motivational interview, the peer recovery coach will remain in contact with participants by phone or in person at least once a week over the following 6-month period and help with facilitating linkage to HIV pre-exposure prophylaxis, HCV and substance use care and treatment.

9 Study Procedures

- The study will be conducted at the low-barrier walk-in clinic at BMC. The clinic sees approximately 500 unique patients annually. After reactive HCV testing at the BMC LBA walk-in clinic, all participants will be linked to care at the BMC General Internal Medicine (GIM) clinic. Participants will be followed for 6 months.
- Recruitment: Participants will be recruited through flyers posted at the LBA walk-in clinic and brief information provided at intake.
 - Flyers advertising the study will be placed in the waiting and common areas of the BMC LBA clinic.

A trained RA will perform baseline interviews, as well as 3- and 6-month post enrollment face-to-face interviews using assessments listed in Table 1. The RA will also review the electronic medical records (EMR) to obtain clinical data (HIV and HCV-related test results) as well as information on appointments. If we are not able to perform in-person interviews, then assessments will be performed over the phone, if possible. For each participant we will determine:

- (1) The proportion of participants with linkage to care.
- (2) The proportion of participants retained in care

H-39712: Peer Recovery Coaching for Infectious Diseases and Opioid Use Disorder
Version 1.1 07/07/2020

(3) The following additional outcomes:

HIV PrEP-related outcomes: Testing for sexually transmitted diseases including HIV, gonorrhea, chlamydia, syphilis, and hepatitis B and C.

HCV continuum of care outcomes: HCV RNA testing, liver fibrosis staging, treatment initiation and cure.

Opioid use disorder treatment-related outcomes: The proportion of individuals with repeat medication for opioid use disorder (MOUD) clinic visits and/or repeat prescriptions for opioid use disorder including buprenorphine and naltrexone, or linked to methadone treatment.

Table 1: List of data to be abstracted

Characteristic	Description
Demographics	Age, gender, employment, housing, social support
HIV PrEP clinical information	HIV antibody, STI testing, prescription for PrEP
HCV clinical information	HCV viral load, genotype, fibrosis staging, HCV treatment
HIV PrEP, HCV care, Addiction services	Appointments attended
Drug Use	Types, ASI ²² , dependence by CIDI-SF ²³ Urine testing, MOUD prescription
Readiness to change ruler	Self-assessment on readiness to change behavior and enter treatment
Mental Health and Social	Depression symptoms, stigma and disclosure

*ASI=Addiction severity index; CIDI-SF=Composite International Diagnostic Interview Short Form; MOUD=Medication for opioid use disorder; PrEP=preexposure prophylaxis; STI=Sexually Transmitted Infection

10 Assessment of Safety and Data Safety Monitoring Plan (DSMP)

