4.1 Study Objectives

The goal of the current proposal is to determine the feasibility and acceptability of a peer recovery coaching (PRC) intervention to improve infectious diseases (HIV/HCV) prevention and care alongside treatment for opioid use disorder.

Aim 1: To implement a pilot peer recovery coaching intervention at a walk-in low-barrier bridge clinic to increase uptake of a comprehensive intervention for HIV PrEP, HCV and substance use treatment among PWID accessing care at Boston Medical Center (BMC).

Aim 2: To determine the feasibility and acceptability of a combined PrEP, HCV and substance use treatment intervention at the BMC FASTER PATHS bridge clinic

We hypothesize that the peer recovery coaching intervention will facilitate both access to PrEP, HCV treatment and sustained engagement with treatment for opioid use disorder among participants. The primary outcome is patient satisfaction as a measure of the intervention's acceptability. Secondary outcomes will include (1) the proportion of patients with linkage to PrEP and treatment initiation within 3 months; (2) the proportion of patients with HCV treatment initiation within 3 months; (3) the proportion of patients with sustained linkage to opioid use treatment within 3 months (follow-up with at least one subsequent visit after the initial prescription for medication for opioid use disorder).

H-39712: Peer Recovery Coaching for Infectious Diseases and Opioid Use Disorder
Version 1.1 07/07/2020

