4.1.1 Primary Outcome Measures

This is an open pilot study. The Primary outcome will include patient satisfaction as a measure of the peer recovery coach intervention's acceptability.

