4.1.2 Secondary Outcome Measures

Secondary outcomes will include the following:

- (1) The proportion of participants with linkage to care.
- (2) The proportion of participants retained in care
- (3) The following additional outcomes:

HIV PrEP-related outcomes: Testing for sexually transmitted diseases including HIV, gonorrhea, chlamydia, syphilis, and hepatitis B and C.

HCV continuum of care outcomes: HCV RNA testing, liver fibrosis staging, treatment initiation and cure.

Opioid use disorder treatment-related outcomes: The proportion of individuals with repeat MOUD clinic visits and/or repeat prescriptions for opioid use disorder including buprenorphine and naltrexone, or linked to methadone treatment.

5 Study Design

The study is prospective open pilot study (N=40).

We will include 40 persons with a history of substance use recruited from the BMC FASTER PATHS bridge clinic, a facility caring for approximately 500 unique patients annually. The BMC FASTER PATHS bridge clinic provides universal HIV and HCV testing at the initial clinic intake. After reactive HCV testing, patients are linked to care at the BMC General Internal Medicine (GIM) primary care clinic.

The goal of the current study is to determine feasibility and acceptability of a peer recovery coaching intervention to improve the uptake of HIV prevention, HCV treatment

H-39712: Peer Recovery Coaching for Infectious Diseases and Opioid Use Disorder
Version 1.1 07/07/2020

and substance use treatment at a low-barrier bridge clinic. Along with the research assistant, the peer recovery coach is part of the research staff. The peer recovery coach will carry out the intervention (ie. use motivational interviewing to help participants address their history of opioid use while also accessing treatment for hepatitis C and HIV prevention methods). The peer recovery coach will carry out a baseline motivational interviewing intervention with participants and they will continue to follow the participants over a 6-month time frame. Frequency of follow-up calls will vary depending on the participant's need. The recovery coach will initially start with weekly calls.

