11.3 Case Report Forms

The study case report form (CRF) will be the primary data collection instrument for the study. All data requested on the CRF will be recorded. All missing data will be explained. If a space on the CRF is left blank because the procedure was not done or the question was not asked, "N/D" will be written. If the item is not applicable to the individual case, "N/A" will be written. All entries will be printed legibly in black ink. If any entry error has been made, to correct such an error, a single straight line will be drawn

H-39712: Peer Recovery Coaching for Infectious Diseases and Opioid Use Disorder
Version 1.1 07/07/2020

through the incorrect entry and the correct data will be entered above it. All such changes will be initialed and dated. There will be no erasures or white-out on CRFs. For clarification of illegible or uncertain entries, the clarification will be printed above the item, then initialed and dated. The following source data will be recorded directly on the CRFs: [data where the CRF will be the source document](#).

See the Appendix for the following CRFs: [list one or more CRF by name](#)

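### Patient satisfaction is the only primary outcome, but no scheduled interview is assigned a measure of it, and the planned two-group Wilcoxon test does not fit an open pilot in which everyone is coached

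*Combined protocol and SAP*

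**What the plan says.** Section 4.1 states: "The primary outcome is patient satisfaction as a measure of the" intervention's acceptability. Section 12.1 repeats this. Section 4.1.1 words it as "The Primary outcome will include patient satisfaction as a measure of the peer recovery coach" intervention's acceptability, and 12.3 is similar. No other primary outcome is named anywhere.

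Section 9 describes how data are collected. The research assistant carries out baseline interviews and "3- and 6-month post enrollment face-to-face interviews using assessments listed in Table 1". If a visit in person is not possible, "assessments will be performed over the phone, if possible". Section 6.2 pays participants for each "interview session with the RA at baseline, 3-and 6 months post-enrollment". Table 1 combines data from the medical record with self-reported items, for example a readiness ruler described as "Self-assessment on readiness to change behavior and enter treatment".

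Section 12.3 gives the analysis. After naming satisfaction as primary, it plans recorded semi-structured interviews, with a codebook for acceptability and feasibility applied to every transcript. It then plans descriptive statistics and a Wilcoxon test of 5-point Likert scales between two groups. Only after that does it turn to the secondary outcome, for which it contrasts an intervention group with a current practice group.

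On design, Section 5 says "The study is prospective open pilot study (N=40"). The synopsis before Section 3 has each consenting participant working individually with a coach.

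**The concern.** A primary outcome should be traceable from its definition, through a collection form and a visit, to an analysis. Here the chain breaks in two places.

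The first break is at collection. The section that lists what the interviews use, and what will be determined for each participant, covers the secondary outcomes and leaves out the primary one. Staff who follow it would not be prompted to ask about satisfaction. Most other outcomes can be abstracted later from the medical record, but a satisfaction rating exists only if someone asks for it.

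The second break is at analysis. The only test named for the Likert scales needs two groups of raters, and the design supplies one. With acceptability as a stated goal of the study, both breaks affect its main result.

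**Working it through.** The plan gives no figure for this outcome to reproduce: N=40 comes without a precision target, response rate or satisfaction threshold. The check sets the sections side by side.

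**1. Is satisfaction among the listed assessments?** Table 1 has seven rows: demographics; HIV PrEP clinical data; HCV clinical data; appointments attended; drug use; the readiness ruler; mental health and social. Rows covering satisfaction, acceptability or a Likert item: 0 of 7.

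**2. Is it in the Section 9 list of what will be determined?** The list has three items: linkage to care; retention in care; and additional PrEP, HCV and opioid treatment outcomes. These are the secondary outcomes of 4.1.2. Items covering satisfaction: 0 of 3.

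**3. Could the omission arise because Table 1 is limited to chart data?** No. The readiness ruler and the row on depression symptoms and stigma are self-reported, so the table does hold items that only the participant can supply.

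**4. Does 12.3 supply what is missing?** In part. By their position, the coded interviews and the Likert scales appear to serve the primary outcome.
- What the Likert scales rate: not stated.
- Visit for the scales or for the semi-structured interviews: not stated.
- Who is interviewed, and how many: not stated. Coding every transcript fixes what is analysed once transcripts exist, but not whose they are.
- Primary time point: not stated. By contrast, the three secondary outcomes in 4.1 and 12.1 each carry a 3-month window.

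**5. Does another section fill the gap?** Section 6.2 gives interview times but not content. Section 11.2 names the medical record as the source for linkage and treatment initiation, not for satisfaction. Section 11.3 still reads "list one or more CRF by name" where forms should be named. This last item is context only, and the point does not depend on it.

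**6. How many interviews are affected?** With 40 participants (Section 5) and three interviews each (Sections 6.2 and 9), 40 x 3 = 120 are scheduled. After baseline, when there is coaching to rate, 40 x 2 = 80. Number assigned a satisfaction measure by Table 1 or the Section 9 list: 0 of 80.

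**7. Can the Wilcoxon comparison be carried out?** It needs ratings from two groups. The synopsis, 4.1.1 and Section 5 describe one coached cohort of 40. Section 12.3 mentions a current practice group, but no section gives its source, size, consent or interviews. Its members would also have had no study coaching, so they could not rate satisfaction with it. As the design stands, the second set of ratings does not exist.

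**The case against.** The strongest reply is that Section 9 does not restrict the interviews to Table 1. The table's caption calls it a list of data to be abstracted, and 12.3 describes a separate route to the primary outcome through recorded, coded interviews. This stands, and it limits the conclusion. A reader might infer that the trial will not collect its primary outcome at all. The documents do not support that: they show that no scheduled interview is assigned the measure, while 12.3 intends some measurement at unstated times with unstated people.

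A second reply is that little freedom remains. Satisfaction with coaching cannot sensibly be rated at baseline, so only months 3 and 6 are candidates among the scheduled visits. The study is a pilot, 12.2 disclaims power for efficacy, and no decision rule depends on satisfaction. This also stands, as a limit on the harm from choosing a visit late. It does not answer the missing collection step.

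A reader might also infer that the reported satisfaction will be biased, perhaps upward, because dissatisfied participants drop out. The documents give no expected response rate and nothing to fix a direction, so any figure would rest on assumptions that fit any survey.

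Finally, the appendix lists a schedule of events and endpoint scales by heading only. Attachments may exist that cannot be seen here, so the headings are not evidence of a gap. The mismatch between the primary outcome and Section 9 does not depend on them.

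**Conclusion.** The concern holds in a limited form. The sole primary outcome is absent from Table 1 and from the Section 9 list, and 12.3 leaves open what the Likert scales rate, when they and the acceptability interviews take place, and with whom. Followed as written, up to 80 post-baseline interviews would go ahead without an assigned satisfaction measure, and those ratings could not be recovered afterwards. The Wilcoxon comparison cannot be carried out in the design described.

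The count of 80 assumes that all 40 participants are enrolled and complete both later interviews. The link between the Likert scales and satisfaction is inferred from their place in 12.3. The two groups are taken to be the intervention and current practice groups that 12.3 names next. No claim is made about the size or direction of any bias. Because collection is prospective, this should be settled before the first 3-month interview.

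**What to change.** 1. Add a named 5-point satisfaction item or scale to Table 1 and to the Section 9 list, for the 3- and 6-month interviews, by phone where needed as Section 9 already allows.
2. In 4.1.1 and 12.3, name one of these two visits in advance as the primary time point. Under Section 8, month 3 falls midway through the 6-month coaching period and month 6 at its end, with more time for loss to follow-up; the choice is the sponsor's. State when the semi-structured interviews take place and with whom.
3. Reconcile the two groups in 12.3 with the open pilot. If there is one group, replace the Wilcoxon test with the distribution of ratings and the number responding out of all enrolled participants. If a current practice group is kept, state its source and size, and restrict its satisfaction outcome to what its members can rate.

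Best- and worst-case bounds for non-respondents are optional. Naming the form in 11.3 would be a natural companion edit.

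The cost is the choice of a short measure, its use in at most 80 interviews that are already scheduled and paid for, and edits to 4.1.1, Section 9, Table 1 and 12.3. The downside is slightly longer interviews. No visits or participants are added.

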10.1 Definitions

The following definitions will be used in the assessment of safety:

Adverse Event (AE) is any untoward or unfavorable medical occurrence in a human subject, including any abnormal sign (for example, abnormal physical exam or laboratory finding), symptom, or disease, temporally associated with the subject's

H-39712: Peer Recovery Coaching for Infectious Diseases and Opioid Use Disorder
Version 1.1 07/07/2020

participation in the research, whether or not considered related to the subject's participation in the research.

10.2 Safety Review

Both the risks listed in Section 4.1 and unknown risks will be monitored as follows

Data safety monitoring plan:

The PI will continually monitor the safety of participants and study data. Adverse events and unanticipated problems will be reviewed to detect any trends and threats to participant safety and concerns for breach of participant confidentiality. Additional issues that arise will be routinely monitored by the PI. Any adverse events will be reported to the IRB and the sponsor, as appropriate, and any necessary revisions to the protocol and/or standard operating procedures will be submitted for IRB review.

10.3 Reporting Plans

The Principal Investigator will report Unanticipated Problems and Adverse Events to IRB. Unanticipated Problems occurring at BMC/BU Medical Campus not involving a fatal or life-threatening event will be reported to the IRB within 7 days of the investigator learning of the event. Adverse Events (including Serious Adverse Events) will be reported in summary at the time of continuing review, along with a statement that the pattern of adverse events, in total, does not suggest that the research places subjects or others at a greater risk of harm than was previously known. Reports from safety monitors with no recommended changes will be reported to the IRB at the time of continuing review.

10.4 Stopping Rules

The study has no stopping rules.

Right to Refuse or Withdraw

Participation in the study is voluntary. Participants will have the right to refuse to take part in the study. If a participant decides to take part in the study and then were to change his/her mind, he/she will be able to withdraw from the research. Withdrawing from the study would not impact the care received at BMC.

11 Data Handling and Record Keeping

11.1 Confidentiality

Confidentiality

We will train research staff on the importance of maintaining confidentiality and assuring confidentiality of records. In addition, participants will be assigned a unique study identifier, and their names will not be used. All documents will be kept in locked cabinets in the study office. A master list of subjects' names and code numbers will be stored in a locked file cabinet separate from the rest of the data. Only [name] and the study RA will have access to this information. The list will be destroyed upon completion of the study. All interviews and interventions will be conducted in private locations of the facility. All data will be kept confidential and stored in locked cabinets. Key drives and computers will be password protected.

Certificate of Confidentiality

To help us protect the privacy of participants, we have obtained a Certificate of Confidentiality from the National Institutes of Health. With this Certificate, the investigator cannot be forced to disclose information that may identify participants, even by a court subpoena, in any federal, state, or local civil, criminal, administrative, legislative, or other proceedings.

11.2 Source Documents

We will review patients' electronic medical record at BMC to determine outcomes (linkage to care, initiation of HCV and HIV PrEP and substance use treatment). Data will be directly entered into a RedCap database including all the fields that will be necessary for the study.

